These patients will then be seen during an initial visit by the research nurse. This meeting will take place during their hospitalization, in the patients' respective rooms or in a closed room (if multiple bed in the same room) (in order to avoid any external influence on the consent, in addition to better maintaining the confidentiality of the candidates). The purpose of this visit will be to assess the patient's eligibility for the study, to explain the purpose of the study and its interventions. If the patient wishes to participate in the study, a consent form will be read and signed by the patient (Appendix 2). The consent must meet the same criteria as what is applied in the clinic, or a patient must be able and offer free and informed consent. Substituted consent in the event of incapacity (permanent or temporary) with the most significant relative, at the bedside or by telephone will also be authorized. This form will contain the frequent and serious side effects of the two proposed treatments. All the patients who sign will be randomized in the study, into the TPM or LEV group. The method and location of recruitment will therefore be the same for all patients (intervention and active comparator).

Randomization will be made by random block allocation. A number will be assigned to each patient and will be entered into a software that will allow patient randomization, which can be found on the site: https://www.randomizer.at. Patients will be matched there for their NESIS scores (\geq 4 or <4), their home sites (CHUS or other centers) and the presence of SDH evacuating surgery (yes or no). These factors seem to us to be the ones that could have the greatest impact on the results. When starting the randomization, the software must be blocked in order to allow its use, so no modification of the randomization parameters can be added when the process is going to be started.

As recruitment and randomization take place during hospitalization of patients, no travel or additional testing will be required.

Sampling bias control

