The existence of propagated cortical depolarizations will be assessed by electrocorticography (ECoG) for some operated patients (see below for the detailed procedure) as well as by a surface EEG and a near infrared spectroscopy monitor. These paraclinical examinations will help to rule out a diagnosis of epilepsy and will provide the physiological data necessary for the confirmation of cortical depolarizations.

Side effects will be assessed and graded using CTCAE terminology (Common Terminology Criteria for Adverse Events)³¹.

After a first negative pre-randomization EEG, 2 more EEGs will be performed at 24 hour intervals in order to increase the diagnostic sensitivity of ictal activity. If an EEG is positive, there will be no further EEG. These EEG results will help for further validation of the NESIS score.

Magnetic resonance imaging will be recommended in patients with 3 negative EEGs, in order to rule out another structural cause, such as transient ischemic events. This will remain at the discretion of the clinician, depending on clinical relevance and availability of the examination..

Process

Initial meeting

Patients will be seen during their initial hospitalization following the diagnosis of TNS and their first negative EEG. If SDH evacuating surgery is planned for a patient who has already been randomized, they will be offered the installation of an ECoG monitor during the same surgery. This step will be optional. Subsequently, the patients will be reviewed postoperatively and the intervention will be started if transient neurological symptoms persist.

The meeting will be conducted by a research nurse or a member of the research team. An explanation of the study, drugs, goals, and intended patient involvement will be discussed. At this point, patients will have the choice of whether or not to sign the consent form. They will be given time for reflection, if desired. If the patient is participating in the study, demographic data, clinical characteristics of the subdural hematoma and characteristics of transient neurological symptoms will be collected using a standardized questionnaire (Appendix 3). Thereafter, treatment (TPM or LEV) will be assigned by randomization and started during hospitalization with a planned increase up to

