therapeutic doses according to the protocol below. A notebook containing the information discussed, the contact information and forms (appendix 5) for weekly monitoring of neurological symptoms and side effects will be given.

In parallel, after starting the treatment (TPM or LEV), two other daily EEGs will be performed. If an EEG is positive, there will be no further EEG needed. Additionally, if an EEG is positive, the patient will remain in the same treatment group, however, a subanalysis may compare the correlation between EEG and NESIS score results. In addition, brain magnetic resonance imaging will be recommended for patients with three negative EEGs to rule out an alternative diagnosis, such as transient ischemic events. This test is already part of the usual assessment of transient neurological symptoms with negative EEG and therefore does not represent an additional test for patients. However, this examination will be at the discretion of the clinician, depending on the clinical relevance and availability of the examination.

Electrocorticography

If the patient has TNS preoperatively, the installation of electrocorticography electrodes in the subdural space will be suggested. We anticipate that approximately 5 to 10 patients out of the 56 enrolled will be eligible and be offered this option. This step is optional and will not influence subsequent medical treatment. However, it will help to demonstrate the existence of propagated cortical depolarizations and potentially prove the effectiveness of a non-invasive screening strategy. If the patient agrees, two ECoG strip electrodes will be inserted into the subdural space along with the installation of the subdural drain during the surgery. The electrodes will be located at the level of the upper temporal line and oriented anteroposterior in order to cover the frontal operculum as well as the inferior parietal lobule. This procedure is identical to that carried out routinely in the surgical assessment of patients with epilepsy. The patient will then be transferred to the EEG monitoring unit where a surface EEG and a bi-frontal near infrared spectroscopy monitor will be installed. The patient will then be monitored continuously until at least 5 episodes of TNS are recorded, or for a maximum of 72 hours. The electrodes will then be removed by traction at the bedside and a stitch will be performed under local anesthesia. The data will be analyzed by an epileptologist.

Intervention

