Statistical analysis of the various data will be done with the help of the Statistical Package for the Social Sciences (SPSS) software. Most of the data will be analyzed by members of the research team. If necessary, the statistician of the CRC (Clinical Research Center) will be consulted.

The results will be analyzed by "intension-to-treat" given the expected dropouts in the two treatment groups.

Primary outcome: To assess the efficacy of TPM compared to LEV in the treatment of TNS in the context of SDH with negative EEG. To do this, it will be necessary to compare the rate of complete resolution of symptoms between the two groups. Our study comprising two independent groups and this variable being dichotomous (resolution: yes or no), a Chi-Square test will be used. This same test will also be used to compare the response of TPM in the NESIS versus non-NESIS subgroups and the same comparison with LEV will also

be performed. Subsequently, as sub-analyzes, the decrease in the frequency, intensity and duration of episodes (continuous variables) will also be compared in the two groups using a Student's T-test after validation of assumptions underlying the test.

Secondary outcome: tolerance to the antiepileptics used. To do this, we will analyze the comparison of the dropout rate (dichotomous variable: yes or no) and the side effect rate (categorical variable) using a chi-square test.

Degree of significance

We retained a significance level corresponding to an error α of 5%, whether a value p<0.05. The accepted beta error (β) is 10%, for a power of 90%.

Missing data

Patients with a large number of missing data or not including the data necessary to calculate the primary outcome will be excluded from the study. Those with some missing data that do not allow certain calculations of secondary outcomes will be kept in the study, however, the sample sizes of these analyzes will be clarified during writing.

Oversight mechanism

An independent results and dropout rate monitoring committee will not be necessary. However, monitoring will be carried out by the project team.

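### The surgery stratifier is not defined as done or planned, although surgery is expected after randomisation, and the chi-square test ignores it; balance on one of three named key factors is partly left to chance

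*Protocol*

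**What the plan says.** Protocol, Patient recruitment: allocation is by random blocks, within strata of NESIS score (4 or more, or below 4), "their home sites (CHUS or other centers) and the presence of SDH evacuating surgery (yes or no"). The reason given for the three factors is "These factors seem to us to be the ones that could have the greatest impact on the results". Randomisation follows consent during the hospital stay: "All the patients who sign will be randomized in the study, into the TPM or LEV group". Nothing requires surgery to be done or decided first. The same section says that the randomisation parameters cannot be modified once the process has started.

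Protocol, Process, Initial meeting: "If SDH evacuating surgery is planned for a patient who has already been randomized, they will be offered the installation of an ECoG monitor". For these patients, "the patients will be reviewed postoperatively and the intervention will be started if transient neurological symptoms persist".

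Protocol, Electrocorticography: patients with symptoms before surgery are candidates for electrodes, and the expected number is "approximately 5 to 10 patients out of the 56 enrolled".

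Protocol, Data analysis, Statistics: the analysis is by intention to treat, and for the primary outcome, "this variable being dichotomous (resolution: yes or no), a Chi-Square test will be used". The strata are not mentioned.

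Draining surgery is an item in Table 1 and in the initial form (Appendix 3). The follow-up form (Appendix 4) has no item for it.

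**The concern.** A stratification factor has to be a status that can be read off at the moment of randomisation. Presence of surgery is clear for a patient already operated on. It is unclear for one whose operation is scheduled but not yet done, and the Initial meeting section shows that patients are expected to be operated on after randomisation. One reader would enter 'yes' for a scheduled operation and another 'no', and the protocol supports neither. If the entry is 'no', such patients share a stratum with patients who are never operated on, and their split between arms is left to chance.

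This touches the primary outcome directly. Study drug starts after the operation only if symptoms persist, so the protocol accepts that evacuation alone may end them. Under intention to treat, such a patient would count as resolved in the assigned arm without having taken the drug. With about 15 to 21 NESIS patients per arm, a few of them unevenly split can move the observed difference by several points.

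In addition, the chi-square test does not use the stratifier, so even a well-defined factor would not improve the precision of the comparison as it could.

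**Working it through.** **The plan's own figure.** Sample size, proportions formula: 2N = 4 × (1.960 + 1.282)² × 0.57 × 0.43 / (0.14 − 1)² = 13.93, so 2N = 14 and N = 7 per group, as stated. The protocol then chooses 15 per group. This point disputes none of these figures.

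**Inputs from the protocol.** 56 patients in total, 42 of them NESIS before losses, 30 NESIS analysed (15 per arm); 5 to 10 electrocorticography candidates among the 56; levetiracetam resolution 14%.

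**Assumptions.** The 5 to 10 candidates stand in for patients operated on after randomisation, a number that the protocol does not give. Topiramate resolution is taken as 80%, not the protocol's 100%, and resolution after surgery as q = 60%, 80% or 100% on either drug.

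**Step 1, size of the group.** 5/56 = 8.9% and 10/56 = 17.9%. Pro rata, 5 × 42/56 = 3.75 to 10 × 42/56 = 7.5 of the 42 NESIS patients, and 5 × 30/56 = 2.7 to 10 × 30/56 = 5.4 of the 30 analysed.

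**Step 2, chance imbalance if all are entered as 'no'.** With k such patients among N, in equal arms of n = N/2, P(x in one arm) = C(n, x) × C(N − n, k − x) / C(N, k).

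| N | k | Split | Probability of this split or worse |
|---|---|---|---|
| 56 | 5 | 4:1 | 0.35 |
| 56 | 10 | 7:3 | 0.30 |
| 56 | 10 | 8:2 | 0.08 |
| 42 | 4 | 3:1 | 0.61 |
| 42 | 8 | 6:2 | 0.24 |

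**Step 3, what an imbalance does.** The shift in the observed difference is (imbalance / patients per arm) × the extra resolution due to surgery. If surgery adds 50 points (an assumption), a 3:1 split in arms of 21 shifts it by 2/21 × 50 = 4.8 points and a 6:2 split by 4/21 × 50 = 9.5 points. Either direction is equally likely.

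**Step 4, power at 15 v 15 with 5 later-operated patients.** Simulation at two-sided 5%, uncorrected tests. Free allocation draws the surgery split from the distribution in step 2; balanced allocation fixes it at 3:2 or 2:3. The Mantel-Haenszel statistic is (Σ(x − E))² / ΣV over the two surgery strata, where x, E and V are the observed, expected and variance of the topiramate resolutions.

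| Allocation and test | q = 60% | q = 80% | q = 100% |
|---|---|---|---|
| Free, chi-square | 90% | 90% | 90% |
| Balanced, chi-square | 90% | 90% | 92% |
| Balanced, Mantel-Haenszel | 91% | 92% | 95% |

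The total gain is 1 to 5 points. Balance alone gives about 0 to 2 of them; the stratified test gives most of the rest.

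**The case against.** The strongest reply is that this is one undefined word, with little effect. Much of that stands.

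- **A reader might infer that every later-operated patient is entered as 'no'.** That is certain only where surgery is decided after randomisation, and no baseline stratifier can capture that. For surgery already scheduled, the protocol is silent; if centres enter 'yes', the problem shrinks to the late decisions.
- **A reader might infer a biased comparison.** The documents do not support this. Randomisation balances later surgery in expectation, and chance imbalance is already part of the test's error rate: in null simulations with free allocation, the plain chi-square rejected in about 5% to 6%.
- **A reader might infer a large loss of power.** A rise from about 82% to 93% appears only with 8 later-operated patients among 30, every one of them resolving after surgery, and a change of test as well. Eight of 30 (27%) lies above the 18% that the Electrocorticography section implies at most, so it is not used here. Likewise, an extreme such as four operated patients all on levetiracetam has a probability of only 5% at 15 v 15.
- **A reader might infer that the protocol ranks surgery first, or never records it later.** It names three factors jointly and tentatively. Table 1 lists draining surgery beside items that follow randomisation, patients meet a neurosurgeon at follow-up, and the Confidentiality section allows later access to records. What is missing is a dedicated item in Appendix 4.
- **Adjustment for strata is often left to the SAP.** True, but this protocol already names the test. The definition of the stratifier cannot wait for a SAP written after the software is locked.

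What remains is that the factor is undefined where the protocol itself foresees the ambiguous case, that it cannot be corrected after the lock, and that the named test ignores it.

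**Conclusion.** The point holds as a matter of definition and efficiency. Patient recruitment and Initial meeting do not fit together: the first stratifies on a status that, for patients foreseen in the second, has two possible readings. Under one of them, balance on one of three factors named as potentially most influential is partly left to chance. The cost is modest precision, with no bias in expectation: power of about 90% as planned against 91% to 95% with a defined factor and a stratified test. Most of that comes from the test.

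These sizes rest on 5 later-operated patients among 30 (a proxy near the top of the implied range), on 14% and 80% resolution without surgery, and on 60% to 100% after it. With fewer such patients, or a smaller effect of surgery, the gain approaches zero. The change is worth making because it is nearly free and the definition cannot be supplied after the lock.

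**What to change.** 1. **Patient recruitment.** Before the software is locked, define the third factor as *SDH evacuation done or planned at the time of randomisation (yes/no)*. Patients whose surgical decision is still open are entered as 'no', and the entry is not changed later.
2. **Statistics.** Compare topiramate with levetiracetam in the NESIS group by a Mantel-Haenszel test, or its exact stratified version, on that factor as entered. Use this one factor only: all three binary factors make 8 cells, or 56/8 = 7 patients per cell on average.
3. **Appendix 4.** Add one row for any SDH evacuation since the last contact (yes/no, date), and report it by arm. This is descriptive only, because surgery decided after randomisation cannot be stratified on.

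The cost is one sentence in each of two sections and one form row. No extra patients, visits or staff are needed, and no treatment rule changes. The remaining limit is that late surgical decisions stay unbalanced except by chance.

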Our collection data will take the form of a questionnaire. However, the characterization of neurological symptoms requiring some training, in order to be able to adequately distinguish relevant neurological symptoms (those transient likely caused by SDH) from those unrelated to SDH, the main measuring instrument will be a medical evaluation by a person trained in neurology or neurosurgery. This assessment will be based on a questionnaire (appendix 4), so as not to omit the assessment of all areas relevant to the study. Our study being the first on the subject, no questionnaire already approved in other studies can be used. For these reasons, we have constructed a questionnaire including a part on TNS and another on side effects. Doctors or residents evaluating patients won't forget items and will also be encouraged to further specify the various positive items found during the evaluation.

During the initial visit, a standardized questionnaire including demographic data, characteristics of cSDH and transient neurological symptoms will be completed by a member of the research team using the hospital and patient record (appendix 3). This questionnaire will be administered by a physician, resident or research nurse. We consider that characterization of the current episode at the initial visit will not require full training in neurology or neurosurgery. Indeed, the patient will have already been seen closely by a neurologist or neurosurgeon who will have considered TNS as relevant and secondary to the SDH. However, before administering this questionnaire, the nurse will receive a training, which will be given by a member of the research team.

During follow-ups, by telephone or in clinic, the patient will have in hand his research notebook (appendix 5) in which he will have made a calendar of neurological episodes

that have occurred, or side effects noted. This notebook will limit recall bias and will be analyzed as a secondary outcome, in order to compare the reliability of the information noted by patients with that reported by doctors. Subsequently, an assessment by a resident, neurologist or neurosurgeon will be done using the form described above (appendix 4).

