The intervention (Topiramate versus Levetiracetam) will be initiated in the hospital and then, initially, a prescription will be given to the patient for the community pharmacy.

Topiramate will be initiated at 50 mg BID, with an expected increase of 50 mg per week until symptoms are controlled or up to a maximum titration of 100 mg BID.

Levetiracetam will be initiated at 500 mg BID, with an expected increase of 1000 mg divided into 2 doses per week until symptoms are controlled or up to a maximum titration of 1500 mg BID.

The drugs could be reduced or stopped after discussion with a doctor because of side effects or no improvement in TNS.

Follow-up

There will be two phone follow-ups (2nd week and 6th month), as well as two clinical follow-ups (2nd and 4th month).

Phone follow-up: Medical evaluation by a resident, neurologist or neurosurgeon participating in the study. The person administering the assessment will follow a standardized questionnaire so as not to omit information relevant to the study. This assessment includes characterization of transient neurological symptoms and investigation of side effects.

Clinical follow-up: The patient will bring his study notebook to the appointment, in which he will have recorded the various TNS or side effects that have occurred in recent weeks. The appointment will be made by a neurologist or a neurosurgeon (all patients will have a meeting with each of the two specialists). The doctor will therefore carry out an evaluation of TNS and side effects, by completing the standardized questionnaire, which will help to limit the missing data.

The last follow-up will take place at 6 months, a date that we have based on the various studies in cortical depression which have demonstrated maximum effectiveness of TPM at 17 weeks²³. As we did experience in our community, we believe that a significant difference could emerge even earlier.

Losses during follow-up: patients who do not come to the follow-up appointment will be contacted again. In the event of a refusal to attend follow-up or a second absence from an appointment, with the patient's consent, a medical assessment may be completed by phone.

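### The notebook-versus-doctor reliability comparison is between two dependent records, so agreement will be inflated and cannot show that either is reliable

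*Protocol*

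**What the plan says.** The protocol's Measuring instrument section covers telephone and clinic follow-ups together and states that "the patient will have in hand his research notebook", with a calendar of episodes and side effects already entered. It then gives the notebook two roles: "This notebook will limit recall bias and will be analyzed as a secondary outcome". The stated aim of that analysis is to "compare the reliability of the information noted by patients with that reported by doctors". The next sentence places the doctor's assessment on the Appendix 4 form after this.

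The Follow-up section schedules four contacts: by phone at week 2 and month 6, and in clinic at months 2 and 4. For the clinic visits it says "The patient will bring his study notebook to the appointment" and goes on: "The doctor will therefore carry out an evaluation of TNS and side effects, by completing the standardized questionnaire". Its phone paragraph does not mention the notebook, but the Measuring instrument section covers phone contacts explicitly.

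The Collection method section says that, after the initial data from the medical record, the remaining data are supplied by the patient or the family. No section has the doctor's form completed before the notebook is used.

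**The concern.** The notebook's two roles conflict. It can reduce recall error in the doctor's assessment only by shaping what the patient tells the doctor. To the extent that it does, the doctor's record stops being a separate measurement against which the notebook can be checked.

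A high agreement figure could then be published as support for the notebook or the questionnaire when it partly reflects one source counted twice. Reliability is a fair question in this trial. The questionnaire is new and purpose-built (Measuring instrument), and the protocol itself notes that confusion and neurocognitive disorder are common in this population (Sampling bias control).

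The problem arises when the data are captured. If only one value is written down at the visit, no later analysis can separate unaided answers from prompted ones, so a statistical analysis plan could not repair it.

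**Working it through.** The protocol states no agreement statistic, target or sample size for this comparison, so there is no figure to reproduce. The check is mainly one of text.

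**What ties the two records together**

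- Informant: the patient or family for both (Collection method).
- Timing: the notebook is filled in first, is in the patient's hand at the contact, and the form is completed after it (Measuring instrument; Follow-up for clinic visits).
- Function: the notebook is meant to improve the recall on which the form depends (Measuring instrument).

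**What keeps them partly apart**

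- The patient holds the notebook. Nothing says that the doctor reads or copies it, and at two of the four contacts the doctor is on the phone.
- The doctor has to separate symptoms likely due to the hematoma from unrelated ones (Measuring instrument).
- The follow-up form tells the assessor to go through every symptom type even when persistence is answered no (Appendix 4).
- The instruments differ. The notebook asks for episodes under 60 minutes (Appendix 5), while the inclusion criterion allows up to 6 hours. Side effects are mild, moderate or severe in the notebook and CTCAE-graded on the form.

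The first list shows that the records are dependent. The second shows that the dependence is incomplete, so disagreement remains possible.

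**Size, for illustration only**

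Let f be the share of the doctor's yes/no entries that follow the notebook, and let k0 be the kappa that the two records would show if made separately, with the same marginals. Write p0 for the observed agreement between separate records and pe for chance agreement.

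- Observed agreement = f + (1 − f) × p0.
- Observed kappa = [f + (1 − f) × p0 − pe] / (1 − pe) = f + (1 − f) × k0, because k0 = (p0 − pe) / (1 − pe).

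Neither f nor k0 is in the protocol; both are assumed and shown over a range.

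| k0 | f = 0 | f = 0.5 | f = 0.8 | f = 1 |
|---|---|---|---|---|
| 0.20 | 0.20 | 0.60 | 0.84 | 1.00 |
| 0.40 | 0.40 | 0.70 | 0.88 | 1.00 |

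Worked cell: 0.5 + 0.5 × 0.40 = 0.70.

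Agreement can rise in this way with no gain in accuracy. Suppose two yes/no reports are each 80% accurate with independent errors. They agree in 0.8 × 0.8 + 0.2 × 0.2 = 68% of cases. If half the entries follow the notebook, agreement is 0.5 × 1 + 0.5 × 0.68 = 84%, yet both reports are still 80% accurate. With a shared informant the errors would not be independent, so 68% shows the mechanism and is not a realistic baseline.

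**The case against.** A reader might infer that the comparison is circular and agreement built in. The documents do not support that. The notebook is in the patient's hand, not the doctor's; the last contact, at month 6, is by phone; and the doctor filters for relevance and re-questions. Only the f = 1 column gives complete agreement, and nothing in the protocol says that every entry is copied. A discrepancy could even be informative, for example when the doctor rejects or adds an episode.

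A reader might also infer that the primary endpoint loses its validation. The protocol never offers the comparison for that purpose. It names the medical evaluation as the main measuring instrument, and the comparison can equally be read as a check of the patients' notes against the doctor.

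It can further be said that the outcome is slight: it appears in one clause and is absent from the Secondary outcomes list and the Statistics section. A last objection is that an unaided interview still questions the person who wrote the notes, so it sets memory against notes and mixes recall error with the doctor's judgement.

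All of this stands as a limit on the point. It does not restore independence: the notebook is a recall aid at phone contacts as well as in clinic, and the form follows it.

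**Conclusion.** The point holds in a limited form. The notebook and the doctor's form are not independent measurements, and their agreement will be higher than the same two instruments would give if completed separately. A high figure cannot be taken as evidence that either record is reliable.

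The direction rests on the protocol's own text, on the understanding that the recall aid works as intended and influences at least some answers. The size is unknown, because the share of answers so influenced is not documented; the kappas above are illustrations.

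The treatment comparison is not affected, and nothing here argues against using the notebook to help patients recall episodes. This is a low-priority improvement to a minor secondary outcome.

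**What to change.** On Appendix 4, Part 1, add a second column. First record persistence of transient neurological symptoms (yes/no) and the number of episodes from the interview, with the notebook closed. Then have the patient consult it, and record the final value in the second column. Use the final value for efficacy, which keeps the benefit for recall. Compare the unaided value with the notebook, and state in the report that both still come from the same informant. This reduces the dependence without removing it, and by phone the assessor can only ask that the notebook stay closed.

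If the form is not to be changed, report the comparison only as concordance between dependent sources, or withdraw it.

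The cost is one extra column and, by estimate, about a minute per visit. With four contacts for each of 56 patients that is at most 4 × 56 = 224 minutes, under four hours over the whole trial.
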